5.1 Assignment of Analysis Sets

The complete study population will be defined by the study inclusion and exclusion criteria. However, subsets of the complete study population will be used to address certain study objectives. The analysis sets for the *first eligible IUD insertions* are outlined in Table 2. The analysis sets for subsequent IUD insertions will be defined in the same way for the corresponding IUD insertions.

Table 2. Women Included in Analysis Sets 1 and/or 2

Event in Electronic Health Record	Postpartum Status	Breastfeeding Status ^a		
		Yes	No	Undetermined
Delivery in the past year (52 weeks)	≤ 6 weeks	1, 2	1, 2	1
	> 6 weeks and ≤ 14 weeks	1, 2	1, 2	1
	> 14 and ≤ 52 weeks	1, 2	1, 2	1
No evidence of delivery in the past year	No delivery in the past 52 weeks	NA	1	NA

NA = not applicable.

^a The numbers indicate the analysis set numbers.

5.1.1 Analysis Set 1: Complete Study Population

This analysis set will include women with eligible insertions based on study inclusion and exclusion criteria outlined in Section 3 and in the study protocol. This analysis set will include women with missing data for breastfeeding status and/or IUD type for the insertion. The missing data within breastfeeding status and IUD type may be considered a separate group in the analyses (e.g., when developing the propensity score model for postpartum period).

5.1.2 Analysis Set 2: Breastfeeding Status Available

Women who were less than 52 weeks postpartum at the time of IUD insertion and have either “yes” or “no” breastfeeding status at the time of IUD insertion will be included in this analysis set. Women who have undetermined breastfeeding status for the insertion will not be included.

5.1.3 Analysis Set 3: IUD Type Available

Women with a known type of IUD (either LNG-IUD or copper IUD) for the insertion will be included in this analysis set. Women who have an undetermined IUD type for the insertion will not be included.

6 Statistical Methodology

All analyses will be conducted and/or presented using the pooled data and by data source, as appropriate. However, due to the expected sparse outcomes and the data source restriction on reporting IUD type, some analyses will be conducted using only the pooled data, not by data source. In addition, if sparse cells (i.e., count < 10 for exposures, covariates, or outcomes) are identified during the analysis, the sparse cells may be combined into other meaningful categories, excluded from analysis, or left as they are. Decisions will be made by the study team at the time sparse cells are identified.

Objectives and the corresponding exposures, outcomes, analysis sets, and insertions (e.g., first insertions or subsequent insertions) are summarized in Sections 9.1 and 9.2. Propensity score models and the corresponding objectives are summarized in Section 9.3. A list of tables and figures is included in Section 9.4. Table shells are provided as a separate document and are embedded in Section 9.5.

6.1 Population Characteristics

Descriptive analyses will be conducted to describe baseline demographics and clinical characteristics at the time of the IUD insertion among the three analysis sets (Analysis Tables 0.1.1 through 0.6.5). Separate tables will be generated for the pooled study population and for each of the

four databases. Characteristics will be presented overall and for each outcome category of the two study endpoints, perforation and expulsion.

Important characteristics that will be summarized are as follows:

- Demographics (age at index date, race/ethnicity)
- Clinical characteristics (BMI, dysmenorrhea, parity, previous cesarean delivery)
- Procedure-related characteristics (indicator for concomitant procedure and indicators for a difficult IUD insertion [cervical dilation, ultrasound guidance])
- Provider-related characteristics (number of IUD insertions performed)

All variables to be included in the descriptive analyses are described in Sections 3 and 4.6 and listed in the table shells in Section 9.5. Categorical variables will be summarized using frequencies and percentages, and continuous variables will be summarized using means, standard deviations, medians, lower quartiles, upper quartiles, and minimum and maximum values, as described in Section 4.1.1.

Analysis Tables 0.1.1 through 0.3.5 will present demographic summaries for the primary analysis population, which includes only the first observed IUD insertion. Because a woman can have only one eligible insertion in the primary analyses, Analysis Tables 0.1.1 through 0.3.5 will be at the patient level. Analysis Tables 0.4.1 through 0.6.5 will present demographic summaries at the insertion level for the secondary analysis population, which includes all subsequent IUD insertions. Because the unit of observation in the secondary analyses is an IUD insertion, if a woman has more than one eligible insertion during the study period, she will be included more than once in the columns of Analysis Tables 0.4.1 through 0.6.5, with baseline demographic characteristics summarized at each index date. These tables will include number of patients or insertions, as well as number of person-years at risk.

6.2 Analysis of Primary Variable(s)

The primary endpoint in the study is time to diagnosis of uterine perforation (defined in Table 1). Study objectives related to uterine perforation and the corresponding exposures and analysis sets are summarized in Section 9.1. A list of planned analysis tables and figures is included in Section 9.4.

6.2.1 Analysis for Primary Objectives

In the following groups of women, the adjusted hazard ratios for uterine perforation will be evaluated:

- Objective 1. Women who were breastfeeding at the time of the first observed IUD insertion versus those who were not breastfeeding at the time of the first observed IUD insertion.
- Objective 2. Women who had a first observed IUD insertion within different time periods postpartum (i.e., ≤ 6 weeks, > 6 weeks and ≤ 14 weeks, > 14 weeks and ≤ 52 weeks) versus those who had a first observed IUD insertion late in the postpartum period (more than 52 weeks postpartum, including those without recorded delivery in the past 52 weeks).

For objective 1, analyses will be conducted using Analysis Set 2 (breastfeeding status is available). For objective 2, analyses will be conducted using Analysis Set 1 (complete study population). Both analyses will use only the first observed IUD insertion.

Cox regression models will be used to obtain crude hazard ratios overall and by data source with assessment of the proportional hazards assumption (Section 4.1.4).

Confounding effects will be adjusted using the propensity score weighting method (Section 4.1.5). After developing the propensity score model, calculating the weights, and assessing the balance between exposure groups in the weighted sample, adjusted hazard ratios will be estimated using the weighted Cox regression model as described in Section 4.1.6. Additionally, the interaction effect between the data source and the exposure will be assessed after adjustment for confounding. The interaction will be assessed by including terms for exposure, database, and the interaction between the database and the exposure in the weighted Cox models. A type 3 group test for the interaction terms will be conducted. If the test is statistically significant ($P < 0.05$), then the interaction terms will be retained in the final model, and the adjusted hazard ratios will be reported for each data source. If the interaction terms are not statistically significant, then the interaction terms will be removed, and the overall adjusted hazard ratios (the main effect) will be reported as the results of the primary analyses.

Two-sided 95% CIs of the adjusted hazard ratios for uterine perforation will be presented overall or by data source, as appropriate. If the exposure-by-data source interaction is not significant, then the corresponding two-sided test of the null hypothesis that the natural logarithm of the overall adjusted hazard ratio equals 0 will be performed. The significance level of 0.05 will be applied. There will be no adjustment for multiplicity.

As a sensitivity analysis, confounding effects will be accounted for by including selected key covariates in the unweighted Cox models. The Cox models will include exposure, site, exposure-by-site interaction, and baseline covariates. Due to the sparse outcomes, limited covariates will be selected for inclusion based on their association with the study outcome. The sensitivity analysis will be conducted only for the primary objectives.

Planned Analysis Tables 1.1 (for breastfeeding status) and 2.1 (for postpartum status) will present crude hazard ratio and hazard ratio adjusted via overlap weighting. Analysis Tables 1.2.1 through 1.3.5 and 2.2.1 through 2.3.5 will present baseline characteristics by exposure and standardized differences (described in Section 4.1.5) prior to and after overlap weighting. Analysis Tables 1.4 and 2.4 will present hazard ratios adjusted by including baseline covariates in the model. Results related to the development of propensity score models will be presented in Analysis Tables 33.1.1, 33.2.1, 33.2.2, 33.3.1, 33.3.2 and Analysis Figures 33.1.1 and 33.1.2.

6.2.2 Analysis for Secondary Objectives

6.2.2.1 Crude Incidence Rates and Cumulative Incidence

Crude incidence rates during follow-up and crude cumulative incidence at year 1 and year 5 for the first observed IUD insertions will be calculated overall and by exposure groups (objectives 3-7, as described in Sections 4.1.2 and 4.1.3). Analyses will be conducted using the pooled data and by data source (Analysis Tables 3.1 through 5). Due to data source restrictions, any results on type of IUD by data source will not be reported.

Additionally, the cumulative incidence curve over time, also known as the failure function (i.e., 1 - survival function), will be estimated using the Kaplan-Meier method and plotted overall for each analysis set (Analysis Figures 3.1 through 7.1).

6.2.2.2 Comparing Adjusted Hazard Ratios Among First Observed IUD Insertions

Adjusted hazard ratios associated with the first observed IUD insertions will be estimated for secondary objectives 14-16, and 19 using the same analysis approach (i.e., overlap weighting) as described in Section 6.2.1, with the following exceptions.

1. For type of IUD, analyses may be conducted by data source. However, due to data source restrictions, any results on type of IUD by data source will not be reported.
2. For secondary objectives that include dichotomization of “early” and “late” postpartum categories, separate propensity score models will not be developed. Rather, the propensity score model developed for the four-category variable will be used. The propensity score for dichotomous exposed group will be calculated by collapsing multiple categories (e.g., propensity score for ≤ 14 weeks = propensity score for ≤ 6 weeks + propensity score for > 6 to ≤ 14 weeks).
3. The analyses for objective 19 (menorrhagia) will be performed only if more than 20,000 IUD insertions with an indication of menorrhagia can be included in the analysis.

Balance will be assessed between exposure groups prior to and after weighting. Crude hazard ratios will also be reported.

The same set of analysis tables and figures as those created for objective 1 will be generated, except that no sensitivity analyses will be conducted for these secondary objectives.

6.2.2.3 Comparing Adjusted IRR and Adjusted IRD

To compare results from this study to those obtained in EURAS-IUD, we will estimate the adjusted IRR and IRD of uterine perforation at 1 year and 5 years of follow-up among women who had a first observed IUD insertion ≤ 36 weeks postpartum versus women who had a first observed IUD insertion > 36 weeks postpartum, including women without recorded delivery within the past 52 weeks (objective 17). Adjusted IRRs and IRDs will be calculated via weighted estimation of the rates using overlap weights as described in Sections 4.1.8 and 4.1.10, respectively.

Using the final analysis datasets after propensity score development and weighting, we will calculate adjusted IRRs and IRDs for the study outcomes. Tables will display the weighted number of outcomes, total weighted person-years, and weighted incidence rates for women who had a first observed IUD insertion ≤ 36 weeks postpartum and for women who had a first observed IUD insertion > 36 weeks postpartum. The adjusted IRRs and IRDs along with 95% CIs will be displayed. Analysis Tables 17.1 will be created for uterine perforation.

6.2.2.4 Comparing Adjusted Hazard Ratios for Subsequent IUD Insertions

Adjusted hazard ratios associated with subsequent IUD insertions will be estimated for secondary objectives 18. These analyses will be conducted using the same analysis approach (i.e., Cox models with overlap weights) described previously for first insertions except using subsequent IUD insertions.

Propensity score models will be developed using subsequent IUD insertions. IUD insertion count (the sequential number) may be included in the propensity score model, as needed. To account for the correlation within women with multiple IUD insertions, a robust, sandwich-type variance estimator will be used to calculate 95% CIs. This will be conducted by using the COVSANDWICH

option in the PROC PHREG procedure in SAS. This is the same variance estimator to account for the fact that the weights are estimated.

The site-specific analyses will be performed only if there are more than 20,000 subsequent IUD insertions for that site. The pooled analysis will include all sites regardless of the number of subsequent IUD insertions at individual sites. The crude and adjusted hazard ratios and 95% CIs will be reported.

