17	By ≤ or > 36 weeks postpartum	X		
Adjusted hazard ratio for IUD expulsion				
25	By ≤ or > 36 weeks postpartum	X		

9.7.3.4.3 Comparing adjusted hazard ratios for uterine perforation and IUD expulsion among subsequent IUD insertions

Estimation of adjusted hazard ratios associated with subsequent (i.e., not the first) IUD insertions will be conducted for secondary objectives 18 and 26 in Section 8.2.

These analyses will be conducted similarly to those described in Sections 9.7.3.4.1 and 9.7.3.4.2. Options to account for correlation within women with multiple IUD insertions will be explored for use with models for subsequent insertions to account for the inclusion of multiple IUD insertions per woman. If correlation among insertions within a woman cannot be adequately addressed, then descriptive analyses will be conducted for assessment of subsequent IUD insertions within a woman.

Pooled analysis will include all sites regardless of the number of subsequent IUD insertions at a site. Site-specific analyses will be performed only if there are more than 20,000 subsequent IUD insertions for that site.

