4.1.4 Crude Hazard Ratios

Crude hazard ratios will be estimated using Cox regression models. These crude hazard ratios will be calculated for each outcome without adjustment for covariates. All crude hazard ratios will be reported as point estimates with 95% CIs.

The proportional hazards assumption between each exposure-outcome pairing will be assessed using visual examination of hazard functions, log-log survival curves, and goodness-of-fit testing using Schoenfeld residuals (Kleinbaum and Klein, 2012). Parallel hazard function and log-log survival curves for exposure groups (i.e., the vertical distance between exposure groups is constant) would indicate that the assumption of proportional hazards is met. The hazard function and log-log plot will be generated using the PLOTS=(H LLS) option in the PROC LIFETEST procedure in SAS. The goodness-of-fit global correlation test based on Schoenfeld residuals will be conducted using the ZPH(GLOBAL) option in the PROC PHREG procedure in SAS. A test with $P < 0.05$ will indicate that the proportional hazards assumption does not hold. If both visual examination and the global correlation test suggest nonproportional hazards, the time-dependent exposure covariate will be included in crude and adjusted hazard ratio models by fitting interaction terms with continuous or categorical time (Paul, 1995). The form of the interaction terms will be determined after reviewing the plots of hazard functions and log-log survival curves. An example SAS program code follows, where *brstime* is the time-dependent exposure covariate created with the programming statement in the PHREG procedure as an exposure-by-time interaction:

```
PROC PHREG DATA=start;
  CLASS brstfeed;
  MODEL personyr * outcome (0) = brstfeed brstime / TIES=EFRON;
  brstime = brstfeed * (personyr > 0.5); /* use 0.5 as an example*/
RUN;
```

For any models including time-dependent exposure covariates, separate hazard ratios will be reported for estimates of the effect of the exposure over time.

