4.1.6 Adjusted Hazard Ratios

The adjusted hazard ratios and 95% CIs will be estimated using weighted Cox regression models. Hazard ratios will be adjusted for possible confounding effects using overlap weighting (Section 4.1.5). This will be conducted in SAS using PROC PHREG with the WEIGHT statement. Normalized weights will be used for the weighted Cox models. The normalized weights add up to the sample size, so that the estimated covariance matrix of the parameter estimators is invariant to the scale of the weights. To account for the fact that the weights are estimated, a robust, sandwich-type variance estimator will be used to calculate 95% CIs. This will be conducted by using the COVSANDWICH option in the PROC PHREG procedure in SAS. Adjusted hazard ratios will be reported as point estimates with 95% CIs.

Time-dependent exposure covariates will be included if violation of the proportional hazards assumption is identified in the unweighted Cox model (described in Section 4.1.4.).

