6.3 Analysis of Secondary Variable(s)

6.3.1 Analysis of IUD Expulsion

The secondary endpoint in the study is time to diagnosis of IUD expulsion (defined in Table 1). In the following groups of women, the adjusted hazard ratios for IUD expulsion will be evaluated:

- Objective 20. Women who were breastfeeding at the time of the first observed IUD insertion versus those who were not breastfeeding at the time of the first observed IUD insertion.
- Objective 23. Women who had a first observed IUD insertion within different time periods postpartum (i.e., ≤ 6 weeks, > 6 weeks and ≤ 14 weeks, > 14 weeks and ≤ 52 weeks) versus those who had a first observed IUD insertion late in the postpartum period (more than 52 weeks postpartum, including those without recorded delivery in the previous 52 weeks).

Study objectives related to IUD expulsion and the corresponding exposures and analysis sets are summarized in Section 9.2. Analyses will be the same as those for uterine preformation, as described

in Section 6.2, except (1) no sensitivity analyses will be conducted and (2) assessment of effect modification using a Cox model including breastfeeding status, early (≤ 14 weeks) versus late (> 14 weeks) postpartum status, and their interaction will not be conducted.

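### SAP 6.2.2.4 says the sandwich variance handles repeated insertions within a woman, but it names no woman-level grouping, so the intervals for objectives 18 and 26 would not account for the clustering as specified

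*SAP*

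**What the plan says.** Protocol 9.7.3.4.3 leaves the method open: "Options to account for correlation within women with multiple IUD insertions will be explored for use with models for subsequent insertions". It adds a fallback: if the correlation cannot be handled adequately, the assessment becomes descriptive.

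SAP 6.2.2.4 settles on a method: "To account for the correlation within women with multiple IUD insertions, a robust, sandwich-type variance estimator will be used to calculate 95% CIs". It names the COVSANDWICH option in PROC PHREG and continues: "This is the same variance estimator to account for the fact that the weights are estimated". The SAP does not repeat the fallback.

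The estimator referred to is in SAP 4.1.6, where a robust variance allows for estimated weights: "This will be conducted by using the COVSANDWICH option in the PROC PHREG procedure in SAS". Neither section mentions a woman identifier, an ID statement or aggregation.

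The unit of analysis is the insertion. SAP 6.1 says: "Because the unit of observation in the secondary analyses is an IUD insertion, if a woman has more than one eligible insertion during the study". Such a woman is counted more than once. Table Layout 1 has rows for insertion counts of 1, 2, 3 and beyond. A woman who reaches a count of 3 contributes at least two records to the subsequent-insertion set.

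SAP 6.2.2.4 names only objective 18. Objective 26 (expulsion) is reached through SAP 6.3.1, "Analyses will be the same as those for uterine preformation, as described" in Section 6.2, with two exceptions that do not concern clustering, and through the table in SAP 9.2.

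**The concern.** A sandwich variance allows for correlation among a woman's records only if her score residuals are added together before they are squared. That step needs to know which records belong to the same woman. The SAP claims the property but specifies the estimator used where each woman has one record, and says the two are the same. A programmer following the text would treat each subsequent insertion as independent.

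If insertions in the same woman are positively correlated, and her exposure tends to stay the same, the intervals for objectives 18 and 26 would be somewhat too narrow. The protocol's condition for going beyond descriptive analysis, that the correlation be adequately addressed, would also be treated as met by a specification that does not meet it.

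**Working it through.** The documents give no standard error, cluster-size distribution or expulsion rate for these objectives, so there is no stated figure to reproduce.

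**1. The two estimators.** Let *L* be the weighted score residual of a record and *I* the information.
- Summed per record: SE = √(Σ *L*²) / *I*, over records.
- Summed per woman: SE = √(Σ (Σ *L*)²) / *I*, with the inner sum over a woman's records and the outer sum over women.

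They coincide when each woman has one record, as in SAP 4.1.6. They differ by the within-woman cross-products, which is where the correlation enters.

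**2. Duplication test.** A weighted Cox model was fitted to 5,000 simulated women with one record each, and again with every record entered twice under the same woman. The copy adds no information, so a correct SE should not move.
- Per record: 0.0735 fell to 0.0520, a ratio of 0.707 (1/√2 = 0.707).
- Per woman: 0.0735 stayed at 0.0735, a ratio of 1.000.

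This tests the formulas; it was not a SAS run.

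**3. Size of the set.** Protocol 9.5 expects 225,000 first insertions, about 90% of all insertions. Subsequent insertions are then about 225,000 / 0.9 × 0.1 = 25,000. At 1.3 per 1,000 that is 25,000 × 0.0013 = 32.5, about 33 perforations.

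**4. Which cluster sizes fit.** Protocol 9.2.3 expects 6% to 15% of the study population to have more than one insertion. Three assumed splits of women with 1/2/3 subsequent insertions were tried:
- 85/12/3%: mean 1.18; 25,000 / 1.18 = 21,186 women, 9.4% of 225,000. Inside the range.
- 50/30/20%: mean 1.70; 25,000 / 1.70 = 14,706 women, 6.5%. Just inside.
- Three for every woman: 25,000 / 3 = 8,333 women, 3.7%. Outside.

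**5. Simulation.** It used 25,000 insertions, a gamma frailty per woman (variance 1 or 4), exposure constant within woman, no true effect, weights of one, follow-up uniform on 0 to 3 years and 500 replicates. The event rate was 0.0013 per person-year for perforation and an assumed 0.03 for expulsion. With mean follow-up of 1.5 years, the first rate gives about 25,000 × 1.5 × 0.0013 = 49 events, somewhat more than the 33 above. Understatement = 1 − (mean SE per record / mean SE per woman).

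| Split | Frailty variance | Perforation: record vs woman | Understated | Expulsion: record vs woman | Understated |
|---|---|---|---|---|---|
| 85/12/3 | 1 | 0.3225 vs 0.3225 | 0.0% | 0.0670 vs 0.0675 | 0.7% |
| 85/12/3 | 4 | 0.3225 vs 0.3227 | 0.1% | 0.0697 vs 0.0712 | 2.1% |
| 50/30/20 | 1 | 0.3207 vs 0.3210 | 0.1% | 0.0671 vs 0.0685 | 2.0% |
| 50/30/20 | 4 | 0.3235 vs 0.3246 | 0.3% | 0.0697 vs 0.0744 | 6.3% |
| All three | 1 | 0.3205 vs 0.3208 | 0.1% | 0.0670 vs 0.0696 | 3.7% |
| All three | 4 | 0.3272 vs 0.3294 | 0.7% | 0.0697 vs 0.0782 | 10.9% |

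At the expulsion rate with frailty variance 4, coverage of the nominal 95% interval (record vs woman) was 93.2% vs 95.8% for the 50/30/20 split and 92.2% vs 95.4% for three each. With 500 replicates the Monte Carlo error of a coverage figure is about √(0.95 × 0.05 / 500) = 1.0 percentage point.

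**The case against.** The strongest reply is that the SAP states its purpose outright and gives no code for this model. Aggregation by woman is a sub-option of the option already named, so a programmer working to the stated purpose could add it. That is possible, but the text points the other way. It says the estimator is the one used for first insertions. SAP 4 says statistical issues are to be detailed in the SAP, and where a sub-option is meant the SAP writes it out, as with the "ZPH(GLOBAL) option in the PROC PHREG procedure in SAS". The protocol's descriptive fallback does not cure this either, because the SAP presents the correlation as handled.

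The reply is stronger on size. Exposures are assessed at each insertion's own index date (SAP 3 and 4.6) and can change between insertions, which weakens the effect. The simulation held them constant, which is unfavourable to the plan. First insertions are excluded, so only women with two or more subsequent insertions create clustering.

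Two stronger readings are tempting, and the documents support neither.
- A reader might use a design effect of 1 + (Σm²/Σm − 1) × ρ with ρ = 0.5. If Σm²/Σm is 1.6, this gives 1.30, so the variance is understated by 1 − 1/1.30 = 23% and the SE by 1 − 1/√1.30 = 12%. Nothing in the documents supports a correlation that high, and the formula takes exposure as constant within woman.
- A reader might infer that expulsion tends to recur and that women who expelled a device are over-represented in this set. The documents give no expulsion rate, recurrence rate or reason for re-insertion. Over-representation alone would not create clustering.

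**Conclusion.** The point holds as a specification error: the method written down does not have the property claimed for it. The likely numerical effect is small. SE understatement was below 1% for perforation in every scenario. For expulsion it was about 1% to 6% with cluster sizes that fit the protocol's 6% to 15%, and about 11% only with three subsequent insertions for every woman, which falls outside that range. These sizes rest on assumed cluster sizes, frailty variances and an assumed expulsion rate of 3 per 100 person-years.

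Only secondary estimation objectives are touched. Planned hypothesis testing is confined to the primary objectives (Protocol 4.9 and 9.9), which use one insertion per woman. The table layout carried over to objectives 18 and 26 prints a P value that would share the same standard error, but the plan ties no hypothesis test to it. The text does not show that the intervals will certainly ignore clustering, only that they would if it is followed as written. The change is worth making because it is nearly free and corrects a stated property in a postmarketing-requirement study.

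**What to change.** In SAP 6.2.2.4:
- Name objectives 18 and 26 together.
- Specify PROC PHREG with COVSANDWICH(AGGREGATE) and an ID statement for the woman's study ID, for both the crude and the adjusted hazard ratios reported there.
- Replace the sentence calling it the same variance estimator with one saying that residuals are summed by woman here, whereas SAP 4.1.6 needs no grouping because each woman has one record.
- Say whether the protocol's descriptive fallback still applies, since the SAP is silent on it.

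The cost is one sub-option, one ID statement and a few lines of text. The woman identifier is already needed to derive the insertion count in SAP 4.6, and no new data are required.
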